8.3.1. Descriptive Analysis

Plasma and urine concentrations and PK parameters will be summarized with descriptive statistics (number, arithmetic mean, standard deviation, coefficient of variation [CV%], geometric mean, geometric CV%, median, minimum, and maximum).

Individual and mean plasma and urine concentration-time curves (both linear and log linear) will be included in the final report.

8.3.2. Statistical Methodology

The primary analysis planned for this study is a mixed effect model that includes treatment as a fixed effect and subject as a random effect. The analysis will be performed on the natural log (ln)-transformed PK parameters (AUC₀₋₁, AUC₀₋₂₄, and C_{max}) and include calculation of

least squared (LS) means and the difference between treatment LS means, as well as their corresponding 90% confidence intervals (CIs). The geometric mean ratios and their 90% CIs of the PK parameter for each treatment comparison will be constructed using the exponentiation of the difference and the CIs from the mixed effect model. The comparisons of interest will be as follows:

- Multiple doses of digoxin coadministered with multiple doses of LOXO-305 versus multiple doses of digoxin alone.
- Multiple doses of digoxin coadministered with a single dose of LOXO-305 versus multiple doses of digoxin alone.

8.4. Safety Analysis

All safety assessments, including AEs, SAEs, vital sign measurements, clinical laboratory results, safety monitoring of serum digoxin levels, physical examination results, concomitant medications, and 12-lead ECGs, will be tabulated and summarized where possible, using descriptive methodology by treatment, as needed, by timepoint. Unless otherwise specified, baseline value is defined as the last non-missing measurement before administration of study drug on Day 1. No formal statistical analyses are planned for the safety data. All safety data will be listed by subject.

Concomitant medications will be coded using the World Health Organization (WHO) Drug Dictionary (WHO Drug Global B3, September 2019). Adverse events will be coded using Medical Dictionary for Regulatory Activities (MedDRA) Version 22.1 (or higher). The incidence of AEs will be presented by severity and by relationship to study drug as determined by the Investigator or designee (Appendix 1 for AE reporting). All TEAEs will be summarized by system organ class and preferred term.

8.5. Data Handling and Record Keeping

Any changes to information in the trial progress notes and other source documents will be initialed and dated on the day the change is made by a CRU staff member authorized to make the change. Changes will be made by striking a single line through erroneous data and clearly entering the correct data (eg, wrong data right data). If the reason for the change is not apparent, a brief explanation for the change will be written adjacent to the change by the CRU staff member.

The Data Management Plan will be approved by the Sponsor.

Data will be validated during data entry by the CRU and verified by the Study Monitor. Data will then be reviewed by the data management group to resolve any outstanding issues. Listings will be generated after the database is cleaned by data management and will be reviewed by the Covance scientific team. The eCRF and ancillary data will be converted into final SAS® datasets following Study Data Tabulation Model or Sponsor-provided specifications. The final datasets structure will be verified using Web Submission Data Manager®, while the dataset content will be peer reviewed by an independent programmer.

The tables, figures, and listings (TFLs) will be programmed per the final SAP. All TFLs will be peer reviewed by an independent programmer. In addition, draft TFLs will be reviewed by the Covance scientific team during the dry run and data review meetings.

The peer review will be performed by independent programmers following the quality control process and programming checklists.

8.6. Quality Control and Quality Assurance

Quality control and quality assurance will be performed according to Covance SOPs or per Sponsor request, and as applicable, according to the contract between Covance and the Sponsor.

9. ADMINISTRATIVE ASPECTS

9.1. Change in Protocol

There will be no alterations in the protocol without agreement between the Sponsor and the Investigator (or designee).

There will be no alterations in the protocol affecting subject safety without the express written approval of the Sponsor, Investigator (or designee), and the IRB (see Form FDA 1572).

9.2. Site Initiation Visit/Investigator Meeting

Prior to the start of the clinical study, the representative(s) of the Sponsor and/or Sponsor will meet with the Investigator (or designee) and appropriate CRU staff to familiarize the Investigator (or designee) and CRU staff with the materials necessary for conducting the clinical study.

9.3. Disclosure

All information provided regarding the study, as well as all information collected/documented during the study, will be regarded as confidential. The Investigator (or designee) agrees not to disclose such information in any way without prior written permission from the Sponsor.

Any publication of the results, in part or in total (eg, articles in journals or newspapers, oral presentations, abstracts) by the Investigator (or designee) or their representative(s), shall require prior notification and review, within a reasonable timeframe, by the Sponsor, and cannot be made in violation of the Sponsor's confidentiality restrictions or to the detriment of the Sponsor's intellectual property rights.

9.4. Monitoring

The Sponsor will designate a Study Monitor(s) who will be responsible for monitoring this clinical trial. The Sponsor's Study Monitor(s) will monitor the study conduct, proper eCRF and source documentation completion and retention, and accurate study drug accountability. To this end, the Sponsor's Study Monitor(s) will visit the CRU(s) at suitable intervals (or may perform activities remotely as per the Monitoring Plan for this study) and be in frequent contact through verbal and written communication. It is essential that the Sponsor's Study Monitor(s) has access to all documents (related to the study and the individual participants) at any time these are requested. In turn, the Sponsor's Study Monitor(s) will adhere to all requirements for subject confidentiality as outlined in the ICF. The Investigator (or designee) and Investigator's staff will be expected to cooperate with the Sponsor's Study Monitor(s), to be available during a portion of the monitoring visit to answer questions, and to provide any missing information.

9.5. Institutional Review Board

In accordance with US Title 21 Code of Federal Regulations (CFR) 56, the protocol, advertisement, ICF, and other information provided to subjects will be reviewed and

Protocol CONFIDENTIAL

Covance Study: 8456071 Protocol Reference: LOXO-BTK-20021

approved by the IRB. The Sponsor will supply relevant material for the Investigator (or designee) to submit to the IRB for the protocol's review and approval. Verification of the IRB unconditional approval of the protocol and the written ICF statement will be transmitted to the Investigator (or designee).

The IRB will be informed by the Investigator (or designee) of subsequent protocol amendments and of serious and unexpected AEs. Approval for protocol amendments will be transmitted in writing to the Investigator (or designee). If requested, the Investigator (or designee) will permit audits by the IRB and regulatory inspections by providing direct access to source data/documents.

The Investigator (or designee) will provide the IRB with progress reports at appropriate intervals (not to exceed 1 year) and a Study Progress Report following the completion, termination, or discontinuation of the Investigator's (or designee's) participation in the study.

9.6. Informed Consent

Written informed consent for the study will be obtained from all subjects before protocol-specific procedures are carried out. The ICF will be approved (along with the protocol) by the IRB and will be acceptable to the Sponsor.

The Investigator (or designee) will explain the nature of the study and the action of the test product. The subjects will be informed that participation is voluntary and that they can withdraw from the study at any time. In accordance with 21 CFR 50, the informed consent process shall be documented by the use of a written ICF approved by the IRB and signed by the subject prior to protocol-specific procedures being performed.

The subject will sign 2 copies of the ICF. One copy will be given to the subject and the other will be maintained with the subject's records.

9.7. Records

The results from data collected at Screening and during the study will be recorded in the subject's eCRF. To maintain confidentiality, the subjects will be identified only by numbers.

The completed eCRFs will be transferred to the Sponsor (or designee). Copies of each eCRF will be retained by the Investigator (or designee). All source documents, records, and reports will be retained by the CRU in accordance with 21 CFR 312.62(c).

All primary data, or copies thereof (eg, laboratory records, eCRFs, data sheets, correspondence, photographs, and computer records), which are a result of the original observations and activities of the study and are necessary for the reconstruction and evaluation of any study report, will be retained in the CRU archives.

9.8. Reference to Declaration of Helsinki/Basic Principles

The study procedures outlined in this protocol will be conducted in accordance with the US CFR governing Protection of Human Subjects (21 CFR 50), Financial Disclosure by Clinical Investigators (21 CFR 54), IRBs (21 CFR 56), and Investigational New Drug Application (21 CFR 312), as appropriate. As such, these sections of US Title 21 CFR, along with the

applicable International Council for Harmonisation Guidelines, are commonly known as Good Clinical Practices, which are consistent with the Declaration of Helsinki.

9.9. Financing and Insurance

Financing and insurance will be addressed in a separate agreement.

11. APPENDICES

Appendix 1: Adverse Event Reporting

Adverse Events

Definition of Adverse Events

An adverse event (AE; or adverse experience) is defined as any untoward medical occurrence experienced by a patient or healthy adult subject, whether or not considered drug-related by the Investigator (or designee). A treatment-emergent adverse event (TEAE) is an AE that starts on or after the first administration of study drug.

The following are all AEs:

- unfavorable changes in general condition
- subjective or objective signs/symptoms
- concomitant diseases or accidents
- clinically significant adverse changes in laboratory parameters observed in a subject during a clinical study

Adverse events comprise all disturbances of general health status, subjective and objective disease symptoms (including laboratory abnormalities that are deemed clinically significant by the Investigator [or designee]), and accidents observed in the context of a clinical trial, irrespective of a possible causal relationship with the administration of the trial substance.

Categorization of Adverse Events

The severity of AEs will be categorized based on the National Cancer Institute Common Terminology Criteria for Adverse Events (CTCAE) Version 5.0 as follows:

- **Grade 1 Mild:** Asymptomatic or mild symptoms; clinical or diagnostic observations only; intervention not indicated
- **Grade 2 Moderate:** Minimal, local, or noninvasive intervention indicated; limiting age-appropriate instrumental Activities of Daily Living (ADL)*
- Grade 3 Severe or medically significant but not immediately life-threatening:
 Hospitalization or prolongation of hospitalization indicated; disabling; limiting self-care ADL**
- **Grade 4 Life-threatening consequences:** An event that puts the subject at immediate risk of death
- **Grade 5:** Death related to AE

Note: Not all grades are appropriate for all AEs. Therefore, some AEs are listed within the CTCAE with fewer than 5 options for grade selection. Grade 5 (death) is not appropriate for some AEs and therefore is not an option.

 $[\]hbox{* Instrumental ADL refer to preparing meals, shopping for groceries, or clothes, using the telephone, managing money, etc.}$

^{**}Self-care ADL refer to bathing, dressing and undressing, feeding self, using the toilet, taking medications, and not bedridden.

The Investigator (or designee) will make a determination of the relationship of the AE to the study drug using a 2-category system according to the following guidelines:

- **NOT RELATED** = The time course between the administration of investigational product and the occurrence or worsening of the AE rules out a causal relationship and another cause (eg, concomitant drugs, therapies, complications, comorbidities) is suspected
- **RELATED** = The time course between administration of investigational product and the occurrence or worsening of the AE is consistent with a causal relationship and no other cause (eg, concomitant drugs, therapies, complications, comorbidities) can be identified

An AE is associated with the use of the drug if there is a reasonable possibility that the experience may have been caused by the drug.

Pregnancy

As information is available, a pregnancy (including pregnancy in female partners of male subjects) diagnosed through End of Study (EOS) or Early Termination (ET; if the subject discontinues from the study and does not complete a follow-up phone call) and for up to 90 days after study drug administration on Day 16 (or last administration of study drug if subject terminates from the study early) should be reported by the Investigator (or designee) via email to Covance or the Sponsor's Clinical Safety Representative within 24 hours of being notified. Covance or the Sponsor's Clinical Safety Representative will then forward the Pregnancy Form to the Investigator (or designee) for completion.

email: [contact]

A subject becoming pregnant while on study drug will immediately be withdrawn from the study and ET study procedures will be performed. The subject or partner should be followed by the Investigator (or designee) until completion of the pregnancy. If the pregnancy ends for any reason before the anticipated date, the Investigator (or designee) should notify Covance or the Sponsor's Clinical Safety Representative. At the completion of the pregnancy, the Investigator (or designee) will document the outcome of the pregnancy. If the outcome of the pregnancy meets the criteria for immediate classification as a serious adverse event (SAE; ie, postpartum complication, spontaneous abortion, stillbirth, neonatal death, or congenital anomaly), the Investigator (or designee) should follow the procedures for reporting an SAE.

Male subjects will be instructed to notify the Investigator (or designee) immediately if they discover their sexual partner is pregnant. In this instance, the partner must provide written consent before pregnancy information can be collected. When a Clinical Research Unit (CRU) becomes aware that the female partner of a male subject is pregnant, they are to contact the Investigator (or designee) immediately (within 24 hours of the CRU staff becoming aware of the event) in addition to notifying Covance or the Sponsor's Clinical Safety Representative via email.

All pregnancies should be recorded on the AE electronic Case Report Form (eCRF; as appropriate), in addition to completion of the required pregnancy forms. If the Investigator (or designee) suspects that a pregnancy was the result of an interaction between the study

treatment and the contraceptive method, in addition to the pregnancy the drug interaction should also be captured as a separate AE.

Definition of Serious Adverse Events

An SAE by the Food and Drug Administration (FDA) definition is any adverse drug experience occurring at any dose that results in any of the following outcomes:

- Death
- A life-threatening adverse drug experience (ie, one that places the subject, in the view of the Investigator [or designee], at immediate risk of death)
- Inpatient hospitalization or prolongation of existing hospitalization
- A persistent or significant disability/incapacity
- A congenital anomaly/birth defect
- An important medical event that may require medical or surgical intervention to prevent 1 of the above outcomes

Important medical events that may not result in death, be life-threatening, or require hospitalization may be considered SAEs when, based on appropriate medical judgment, they may jeopardize the patient or subject and may require medical or surgical intervention to prevent 1 of the outcomes listed in this definition.

Unexpected Adverse Drug Reaction

An AE or suspected adverse drug reaction is considered 'unexpected' if the event is not listed in the Reference Safety Information section of the Investigator's Brochure (IB) or if it is not listed at the specificity or severity that has been observed for an unapproved investigational medicinal product (IMP).

Reporting

The FDA-reportable AEs are AEs that are associated with the use of the drug and represent events that are assessed as serious, related, and unexpected. The FDA-reportable AEs will be reported by the CRU to the Sponsor and the responsible Institutional Review Board (IRB). Final determination of whether an event represents a suspected unexpected serious adverse reaction (SUSAR) will be the responsibility of the Sponsor.

Within 24 hours of when an AE that is potentially FDA-reportable is first recognized or reported, and within 24 hours of any SAE (regardless of whether the event is assessed as related or unrelated to study drug) being first recognized or reported, Covance or the Sponsor's Clinical Safety Representative will be notified by the Investigator (or designee) in writing using the following email address:

email: [contact]

To report the SAE, the completed report form should be sent by email to Covance or the Sponsor's Clinical Safety Representative within 24 hours of awareness. Incoming reports are

reviewed during normal business hours. Additional reporting instructions and the SAE Report Form are provided in the Study Manual.

The IRB will be notified of any FDA-reportable AE within the timeframe required by the IRB. The IRB Serious and Unexpected Adverse Experience Submission Form will be completed and submitted with the copy of the written confirmation or summary of the AE.

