7.2.1. Adverse Events

Adverse event definitions; assignment of severity, causality, action taken, and outcome; and procedures for reporting SAEs are detailed in Appendix 1.

Subjects will be asked a non-leading HDYF? question such as "Have there been any changes in your health status since Screening/since you were last asked?" at the timepoints specified in Appendix 4 (ie, at Screening [after the ICF is signed], at Check-in [Day -1], at each postdose vital sign measurement, and at an appropriate time for all other days). Subjects will also be encouraged to voluntarily report AEs occurring at any other time through the EOS.

Adverse events, whether volunteered, identified by the subject's responses to HDYF? inquiries, or noted on physical examination, ECG, vital sign measurements, or clinical laboratory evaluations, will be recorded throughout the study (ie, from signing of the ICF until EOS [or ET if the subject discontinues from the study and does not complete a follow-up phone call]), either as subject medical history (if the event is reported as beginning prior to signing of the ICF or if the event occurs prior to study drug administration on Day 1 and is assessed as not related to study procedures by the Investigator [or designee]) or as AEs (if the event occurs after signing of the ICF but prior to study drug administration on Day 1 and is assessed as related to study procedures by the Investigator [or designee], or if the event occurs after study drug administration on Day 1 through EOT or ET regardless of relationship to study drug). From EOT or ET through EOS, only AEs assessed as related to study drug by the Investigator (or designee) are to be reported. All SAEs that develop from the time of ICF signing until EOS (or ET, if the subject discontinues from the study and does not complete a follow-up phone call) are to be reported.

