8.6. Safety and Tolerability Assessments

8.6.1. Adverse Events

All AEs will be coded using the Medical Dictionary for Regulatory Activities (MedDRA) Version 23.0 (or higher if a new version is issued during the study). All AEs will be assigned a severity grade using National Cancer Common Terminology Criteria for Adverse Events (CTCAE) Version 5.0 (or higher if a new version is issued during the study).

A treatment-emergent adverse event (TEAE) will be defined as an AE that starts during or after the first dose, or starts prior to the first dose and increases in severity after the first dose.

A treatment related TEAE will be defined as a TEAE with a relationship of related to the study treatment (LOXO-305 and digoxin), as determined by the investigator.

The assignment of TEAEs to treatments will be as follows:

- A TEAE occurring during or after Day 1 dosing will be assigned to 0.25 mg digoxin alone.
- A TEAE occurring during or after Day 8 dosing of LOXO-305 will be assigned to 200 mg LOXO-305 QD + 0.25 mg digoxin QD.

All AEs will be listed. In addition to the data recorded in the database, the listings will include derived onset time and duration. Onset time will be calculated from the time of the last associated dose for TEAEs only. Where the last associated dose is referring to the last dose received prior to the start of a TEAE.

The frequency of subjects with TEAEs and the number of TEAEs will be summarized for the following categories:

- TEAEs (overall, serious, leading to discontinuation, and leading to death) by treatment
- TEAEs by severity and treatment
- Treatment-related TEAEs (overall, serious, leading to discontinuation, and leading to death) by treatment
- Treatment-related TEAEs by severity and treatment

The frequency of subjects will be summarized separately for TEAEs and treatment-related TEAEs by the following:

- System organ class, preferred term, and treatment
- Preferred term and treatment

For the AE data the following rules will apply:

• For the derivation of TEAE status: If the start date/time of an AE is incomplete or missing, an AE will be assumed to be a TEAE, unless the incomplete start date/time or the end date/time indicates an AE started prior to the first dose.

- For the derivation of treatment-related TEAE status: If the study treatment relationship for a TEAE is missing, a TEAE will be assumed to be a treatment-related TEAE.

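### The two adverse-event causality categories leave two of four cases unclassified and conflict with the protocol's own reasonable-possibility standard

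*Protocol*

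**What the plan says.** Protocol Appendix 1 asks the investigator to judge each AE's relationship to study drug "using a 2-category system according to the following guidelines". Each category joins two conditions with an 'and':

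- NOT RELATED: the time course "rules out a causal relationship and another cause (eg, concomitant drugs, therapies, complications, comorbidities) is suspected".
- RELATED: the time course fits a causal link, and "no other cause (eg, concomitant drugs, therapies, complications, comorbidities) can be identified".

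The sentence that follows says that an AE is associated with use of the drug "if there is a reasonable possibility that the experience may have been caused by the drug". It does not say which of the two categories such an event belongs in.

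The causality call is then used elsewhere:

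- Appendix 1 (Reporting) defines FDA-reportable AEs as those that are associated with the drug and also "represent events that are assessed as serious, related, and unexpected".
- Protocol 7.2.1 says that between EOT/ET and End of Study (EOS) "only AEs assessed as related to study drug by the Investigator (or designee) are to be reported".
- Protocol 4.6 and 7.2.1 allow continued follow-up of related events still ongoing at ET or EOS.
- SAP 8.6.1 defines a treatment-related TEAE as one with a "relationship of related to the study treatment (LOXO-305 and digoxin"), as determined by the investigator, and tabulates these separately. A missing relationship is counted as related.

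**The concern.** A two-box system works only if every event fits one box. Here an investigator can meet an event with plausible timing and a second possible explanation, such as a headache after dosing in a subject who has also had repeated blood draws. No rule tells the investigator how to code it. Two investigators, or one investigator on two days, could code the same event differently and both could claim to follow the appendix.

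The definitions also pull against the reasonable-possibility sentence. An event can have a reasonable possibility of drug causation and still be barred from RELATED because something else might explain it.

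At stake is the consistency of the few outputs that rest on this call. One of them is a regulatory reporting trigger. Another is a set of summary tables serving the secondary objective on safety and tolerability.

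**Working it through.** No figure in the plan is in dispute, so the check is a truth table followed by a sort of the rules that use the result.

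**Step 1: coverage of the categories.** Inputs are the two conditions in each Appendix 1 definition.

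| Timing | Other cause | RELATED met? | NOT RELATED met? | Category |
|---|---|---|---|---|
| Consistent | None identified | Yes | No | RELATED |
| Excludes causation | Suspected | No | Yes | NOT RELATED |
| Consistent | Identified | No (other cause) | No (timing) | None |
| Excludes causation | None suspected | No (timing) | No (no other cause) | None |

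Combinations: 2 × 2 = 4. Covered: 2. Uncovered: 4 − 2 = 2.

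**Step 2: does the reasonable-possibility sentence fill the gap?** Take the third row and suppose that a reasonable possibility of drug causation exists. The event is then associated with the drug. FDA-reportable status needs association and also a related assessment. The first holds; the second fails on a literal reading because another cause has been identified. Since both are required, the stricter test controls and the sentence does not cure the conflict.

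**Step 3: what depends on the call.**

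| Rule | Place | Depends on causality? |
|---|---|---|
| AE reporting, Day 1 dosing to EOT/ET | Protocol 7.2.1 | No |
| SAE notification within 24 hours | Protocol Appendix 1 | No |
| All-TEAE summaries and AE listings | SAP 8.6.1 | No |
| FDA-reportable status and IRB report | Protocol Appendix 1 | Yes |
| Non-serious AEs, EOT/ET to EOS | Protocol 7.2.1 | Yes |
| Follow-up of events ongoing at ET or EOS | Protocol 4.6, 7.2.1 | Yes |
| Treatment-related TEAE summaries | SAP 8.6.1 | Yes |

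The post-EOT window runs to the follow-up call, 7 ± 2 days after EOT or ET, so 5 to 9 days.

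**Step 4: does the SAP's missing-data rule help?** Only if the field is blank. An investigator obliged to tick one of two boxes leaves no blank, so the rule does not reach these events.

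**Step 5: which drug is being judged?** The lead-in to the categories refers to study drug, but the definitions refer to investigational product. Protocol 8.2 takes study drug to mean either or both drugs, Table 2 lists both, and SAP 8.6.1 names both. The synopsis heading on investigational products also covers both, whereas Protocol Section 1 applies the corresponding term to LOXO-305 alone. Both drugs are given on Days 8 to 16, which is 16 − 8 + 1 = 9 of the 16 dosing days. On the joint reading digoxin is not another cause on those days; on the LOXO-305-only reading it is.

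**The case against.** The strongest reply is that the gap is real on paper but small in effect, and most of that stands.

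- **Safeguards.** A reader might infer that related events drop out of safety reporting. The documents do not support this. Every AE from Day 1 dosing to EOT/ET is reported whatever its cause, all SAEs are notified within 24 hours, all TEAEs are summarized, and the sponsor makes the final decision on suspected unexpected serious adverse reactions.
- **Two drugs.** A reader might infer that RELATED is almost unattainable during coadministration because digoxin can always be named as another cause. That needs the LOXO-305-only reading, and the weight of the text (Protocol 8.2, Table 2, SAP 8.6.1) favours judging both together. Subjects are healthy and other medication needs approval, which further limits alternative causes. Protocol 1.4.1 also reports events in an earlier interaction study as related to LOXO-305 and rifampin. That is illustrative only, since that study's causality wording is not shown.
- **Direction.** A reader might infer that the treatment-related tables are biased downward. The text does not fix a direction: the third-row event fails NOT RELATED as well, and an investigator guided by the reasonable-possibility sentence would choose RELATED.
- **Status of the definitions.** They are called guidelines, safety is a secondary objective, and its analysis is descriptive.

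What does not stand is the suggestion that judgement fills the gap harmlessly. The appendix offers two conflicting tests and no rule for choosing between them, and a regulatory trigger requires the stricter one.

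**Conclusion.** The categories are wrong as written. They cover two of the four timing and cause combinations and contradict the standard stated directly beneath them. The supportable consequence is inconsistent or wrong causality calls in the four dependent items marked in Step 3.

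Neither the frequency nor the direction of misclassification can be derived from the documents, and no primary pharmacokinetic result is affected. The coverage gap rests only on reading each 'and' as requiring both conditions, and it holds whether investigational product means one drug or both. Which reading applies changes how often the gap would be met, and that wording should be settled at the same time.

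**What to change.** In Protocol Appendix 1:

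- Define RELATED as a reasonable possibility that study drug caused the AE, even if other causes are possible.
- Define NOT RELATED as the absence of such a possibility, so that the two categories are complementary.
- Delete the conditions on absence of another cause and on suspicion of another cause.
- Replace investigational product with study drug, and state whether causality is judged for each drug or for digoxin and LOXO-305 together, consistent with SAP 8.6.1.

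The cost is a wording change in Appendix 1 and the eCRF completion guidance, with possibly a few more events classed as related. Dosing, sampling and sample size are unaffected. SAP 8.6.1 needs no change if the joint assessment is kept; a per-drug assessment would need its treatment-related definition aligned.
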